2. STUDY OBJECTIVES AND ENDPOINTS

The objectives and endpoints of the study are presented in [Table 2-1](#).

Table 2-1. Study Objectives and Endpoints

OBJECTIVES	ENDPOINTS
Primary	
To evaluate the safety and tolerability of single ascending oral doses of kratom relative to placebo when administered in healthy nondependent recreational polydrug users with opioid experience.	Safety will be evaluated through the assessment of AEs, laboratory tests, vital signs (blood pressure, pulse, respiratory rate, oxygen saturation, and body temperature), ECGs, physical examination findings, and C-SSRS.
Secondary	
To evaluate the PK of mitragynine, 7-hydroxy-mitragynine, paynantheine, speciogynine, and peciociliatine following single ascending oral doses of kratom in healthy nondependent recreational polydrug users with opioid experience.
 
The PK endpoints of this study are the following PK parameters of mitragynine, 7-hydroxy-mitragynine, paynantheine, speciogynine, and peciociliatine: C_{max}, T_{max}, AUC_{0-T}, and $AUC_{0-\infty}$. Additionally, dose-normalized PK parameters C_{max}/D, AUC_{0-T}/D, and $AUC_{0-\infty}/D$ will be estimated.
 
To evaluate the PD of single ascending oral doses of kratom in healthy nondependent recreational polydrug users with opioid experience.
 
The PD endpoint of this study is the maximum (peak) effect (E_{max}) over 24 hours for Drug Liking (“at this moment”), assessed on a bipolar (0 to 100 points) VAS.
 
Key secondary PD endpoints are:
 
• Overall Drug Liking VAS (E_{max})• Take Drug Again VAS (E_{max})• High VAS (E_{max}) 
Non-key secondary PD endpoints are:
 
• Balance of Effects
○ Drug Liking VAS (minimum effect [E_{min}], time of maximum effect [TE_{max}], time of minimum effect [TE_{min}], and time-averaged area under the effect-time curve [TA_AUE])• Positive Effects
○ Good Effects VAS (E_{max}, TE_{max}, and TA_AUE)○ High VAS (E_{max}, TE_{max}, and TA_AUE)• Negative Effects
○ Bad Effects VAS (E_{max}, TE_{max}, and TA_AUE)• Other Subjective Effects

OBJECTIVES	ENDPOINTS

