6. STUDY PROCEDURES

An overview of the study activities for each participant is detailed in [Table 6-1](#).

Subjects may leave the clinical site 48 hours following drug administration. However, they may be advised to stay at the clinical site for safety reasons, if judged necessary by an Investigator or delegate in charge. Subjects will return to the clinical site for a Follow-Up Visit on Day 7 ± 2.

Unless otherwise stated in the protocol, the SOPs of the study facilities, which are available for all activities relevant to the quality of the study, will be followed during this study. When the nominal time for multiple events occurs simultaneously, the events will be staggered using their acceptable windows (acceptable windows for each assessment are specified in the following sections of this protocol). When timepoints coincide, procedures should be carried out in the following order:

1. Vital signs (prior to nominal time)
2. ECG (prior to nominal time)
3. PK blood sampling (at nominal time)
4. Pupillometry (following nominal time, immediately following PK blood sampling and prior to other PD assessments)
5. Subjective measures (following nominal time, immediately following pupillometry)

Any deviation from protocol procedures should be noted in the source documentation and compiled for reporting in the Clinical Study Report.

Table 6-1. Schedule of Activities

Day	Screening	Treatment Period			Follow-Up Visit	
		-1	1	2	3	7 ± 2 (EOS/ET)
Subject Review						
Informed Consent ^a	X					
Eligibility Criteria Review	X	X	X			
Demographics	X					
Medical History	X	X				
Medication, Recreational Drug, Alcohol, and Nicotine Use History	X	X				
DSM-5 Diagnostic	X					
Safety						
C-SSRS Questionnaire ^b	X	X			X	X
Height, Weight, and BMI ^c	X					X
Blood Pressure, Pulse, Body Temperature, and Respiratory Rate ^d	X	X	X	X	X	X
Continuous SpO ₂ Monitoring ^e			X			
Spot SpO ₂ ^f	X		X			
Physical Examination ^g	X	X			X	X

^a The latest version of the consent form must be signed prior to subject's inclusion (prior to study drug administration).

^b Details presented in Section [6.1.7](#).

^c At the Follow-Up Visit, only weight and BMI will be measured.

^d Timepoints of each parameter (blood pressure, pulse, body temperature, and respiratory rate) are detailed in Section [6.1.4.1](#).

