6.1.4. Vital Signs

Windows for blood pressure, pulse, body temperature, spot SpO₂, and respiratory rate assessments are presented in [Table 6-2](#). Vital signs will be performed after the subject is in supine position for at least 3 minutes.

Table 6-2. Acceptable Windows for Vital Sign (Blood Pressure, Pulse, Body Temperature, Spot Oxygen Saturation, and Respiratory Rate) Assessments

Elapsed Time	Acceptable Window
Predose	Within 60 minutes prior to study drug administration
> 0 hour and ≤ 24 hours	± 30 minutes
> 24 hours and ≤ 48 hours	± 1 hour

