6.1.4.1. Blood Pressure, Pulse, Body Temperature, Respiratory Rate

Blood pressure, pulse, body temperature, and respiratory rate measurements will be measured as outlined in [Table 6-1](#) and are further detailed in [Table 6-3](#).

Table 6-3. Vital Sign (Blood Pressure, Pulse, Body Temperature, and Respiratory Rate) Recording Schedule

Vital Sign Recording - Scheduled Time Points	Detail of Measures
Screening	Blood pressure, pulse rate, body temperature, and respiratory rate
Day -1	Blood pressure, pulse rate, and body temperature
Day 1: predose	Blood pressure, pulse rate, body temperature, respiratory rate
Day 1: 1, 2, 4, and 6 hours postdose	Blood pressure, pulse rate, and respiratory rate
Day 2: 24 hours postdose	Blood pressure and pulse rate
Day 3: 48 hours postdose	Blood pressure and pulse rate
Follow-up visit/End of Study	Blood pressure and pulse rate

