### **3.3 Study Procedures**

For complete details on the study assessments to be performed for each study period, refer to [APPENDIX A](#).

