## APPENDIX A STUDY SCHEDULE(S)

---

Day	Screening	Treatment Period			Follow-Up Visit	
	-28 to -1	-1	1	2	3	7 ± 2 (EOS/ET)
Subject Review						
Informed Consent 	X					
Eligibility Criteria Review	X	X	X			
Demographics	X					
Medical History	X	X				
Medication, Recreational Drug, Alcohol, and Nicotine Use History	X	X				
DSM-5 Diagnostic	X					
Safety						
C-SSRS Questionnaire 	X	X			X	X
Height, Weight, and BMI 	X					X
Blood Pressure, Pulse, Body Temperature, and Respiratory Rate 	X	X	X	X	X	X
Continuous SpO 2 Monitoring 			X			

 The latest version of the consent form must be signed prior to subject's inclusion (prior to study drug administration).

 Details presented in Section 6.1.7 of protocol.

 At the Follow-Up Visit, only weight and BMI will be measured.

 Timepoints of each parameter (blood pressure, pulse, body temperature, and respiratory rate) are detailed in Section 6.1.4.1 of protocol.

 Continuous monitoring will be performed up to 1 hour prior to study drug administration and will continue for up to 6 hours following study drug administration, or longer if deemed medically necessary. Additional details are presented in Section 6.1.4.2 of protocol.

Day	Screening	Treatment Period			Follow-Up Visit	
	-28 to -1	-1	1	2	3	7 ± 2 (EOS/ET)
Spot SpO 2 	X		X			
Physical Examination 	X	X			X	X
General Biochemistry, Hematology, and Urinalysis 	X	X			X	X
Serology h	X					
12-lead ECG 	X	X	X	X	X	X
Alcohol and Drugs of Abuse Screen h	X	X				
Pregnancy Test h	X	X			X	X
FSH h	X					
AE Monitoring	X	X	X	X	X	X
Concomitant Medication Recording	X	X	X	X	X	X
Pharmacokinetics						
Blood sampling for PK 			X	X	X	
Pharmacodynamics						
Training Session 			X			

 Timepoints are detailed in Section 6.1.4.2 of protocol for spot SpO2.

 A full physical examination will be performed at Screening and at EOS/ET. A symptom-oriented physical examination will be performed as needed at all other timepoints.

 Details are provided in Table 9-1.

 ECG scheduled timepoints are detailed in Section 6.1.4.5 of protocol.

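### Body temperature is a named vital sign in the primary safety endpoint, but the detailed schedule has no reading after dosing, so its planned change from baseline has no scheduled data.

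*Protocol*

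**What the plan says.** Protocol Table 2-1 defines the primary safety endpoint through several assessments, among them "vital signs (blood pressure, pulse, respiratory rate, oxygen saturation, and body temperature". The Protocol synopsis and SAP Table 2-1 carry the same list. SAP 10.3 counts body temperature among the vital signs and plans tables of observed values and change from baseline. SAP 5.3 takes as baseline the last non-missing value before dosing.

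The timing is set in two layers. Protocol Table 6-1, introduced as an overview, has one combined row, "Blood Pressure, Pulse, Body Temperature, and Respiratory Rate", marked at Screening, Days -1, 1, 2 and 3, and follow-up. Its footnote d reads "Timepoints of each parameter (blood pressure, pulse, body temperature, and respiratory rate) are detailed in Section" 6.1.4.1. SAP Appendix A repeats the row and the marks, and its footnote 4 makes the same deferral: "Timepoints of each parameter (blood pressure, pulse, body temperature, and respiratory rate) are detailed in Section 6.1.4.1 of protocol".

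Section 6.1.4.1 points to Table 6-1 for the outline and to Table 6-3 for the detail. Table 6-3 names temperature at Screening, Day -1 and Day 1 predose. For 1, 2, 4 and 6 hours its entry is "Blood pressure, pulse rate, and respiratory rate". For 24 hours, 48 hours and follow-up it lists blood pressure and pulse only.

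**The concern.** The primary objective is safety relative to placebo. A component of that endpoint needs at least one scheduled value after dosing in both arms; without one it says nothing about the drug. Temperature, as scheduled in Table 6-3, describes subjects only before exposure.

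Two consequences follow. The SAP 10.3 change-from-baseline table for temperature would have no scheduled post-dose rows to fill. The study report would also list temperature as part of the primary safety assessment when the plan never schedules it under treatment. Protocol 1.4.1 adds to the mismatch: it counts body temperature among the monitoring practices expected to detect treatment-emergent events, and it includes feeling hot among the commonly reported effects of kratom. Readings not taken during the study cannot be recovered at analysis.

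**Working it through.** There is no sample-size or power figure to reproduce. The check is a count of scheduled time points, followed by a comparison with the SAP.

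**Step 1: which table governs.** The marks in Table 6-1 and SAP Appendix A sit on a row shared by four parameters. The footnotes to that row send the reader to Section 6.1.4.1 for the time points of each parameter, and that section's detailed table is Table 6-3. The count therefore uses Table 6-3.

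**Step 2: count from Table 6-3.**

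| Time point | Blood pressure and pulse | Respiratory rate | Temperature |
|---|---|---|---|
| Screening | yes | yes | yes |
| Day -1 | yes | no | yes |
| Day 1 predose | yes | yes | yes |
| 1, 2, 4, 6 h (4 time points) | yes | yes | no |
| 24 h | yes | no | no |
| 48 h | yes | no | no |
| Follow-up | yes | no | no |

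- Time points before dosing: 3. Time points after dosing: 4 + 1 + 1 + 1 = 7.
- Blood pressure and pulse: 3 of 3 before, 7 of 7 after.
- Respiratory rate: 2 of 3 before, 4 of 7 after.
- Temperature: 3 of 3 before, 0 of 7 after.

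The fifth named vital sign, oxygen saturation, has its own schedule in Table 6-4, with 9 spot readings after dosing (1, 2, 3, 4, 6, 7, 8, 10 and 12 hours). Temperature is the only one of the five with none.

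**Step 3: apply the SAP definitions.** Change from baseline = post-dose value minus the last non-missing value before dosing. With 40 planned subjects, scheduled post-dose values number 40 × 7 = 280 each for blood pressure and pulse, 40 × 4 = 160 for respiratory rate and 40 × 0 = 0 for temperature (full attendance assumed). The change can be formed from scheduled data for none of the 30 kratom subjects (5 × 6) and none of the 10 placebo subjects (5 × 2). Observed summaries before dosing can still be produced.

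**Step 4: look for another source of post-dose values.**

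- Protocol 6.1 allows extra safety assessments at an investigator's discretion, and Protocol 12.3 allows temperature checks for COVID-19. Both are optional.
- Protocol 6.1.3 describes the physical examination by body system and does not name temperature.
- SAP 5.1 generally keeps unscheduled assessments out of descriptive summaries, apart from their use as baseline. Its next sentence, on repeated or unscheduled results, leaves some doubt about whether the one closest to dosing may be shown. Even on that looser reading, the values would be sporadic.

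None of these provides a planned post-dose comparison.

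**The case against.** A reader might infer something stronger: that the two schedules contradict each other, with temperature required on Days 2, 3 and follow-up by one table and omitted by the other. The argument has some textual basis. Section 6.1.4.1 opens "Blood pressure, pulse, body temperature, and respiratory rate measurements will be measured as outlined in" Table 6-1, the combined row is marked on those days, SAP 3.3 says "For complete details on the study assessments to be performed for each study period, refer to" Appendix A, and the heading of Table 6-2 reads "Acceptable Windows for Vital Sign (Blood Pressure, Pulse, Body Temperature, Spot Oxygen Saturation, and Respiratory Rate) Assessments" over windows that run to 48 hours.

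The documents do not support that reading:

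- Table 6-1 is an overview, and a mark on a shared row need not mean that all four parameters are taken that day. The footnotes to the row in both documents defer to Section 6.1.4.1, and the chain ends at Table 6-3. SAP 3.3 leads to Appendix A, which carries the same deferral.
- Respiratory rate shows the same pattern. The shared row is marked on Days -1, 2, 3 and follow-up, but Table 6-3 omits respiratory rate on each. Table 6-3 varies by parameter throughout.
- The Table 6-2 heading also names spot oxygen saturation, which Table 6-4 does not schedule after 12 hours. A shared list of windows does not show that each named item is measured to the last window.

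So the combined row may mislead, but it does not itself schedule post-dose temperature.

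The other objection concerns weight, and much of it stands. The endpoint is descriptive. Protocol 8.3 promises descriptive statistics only. SAP 10.3 is one general sentence covering all vital signs rather than a promise specific to temperature. No stopping or maximum-tolerated-dose rule uses temperature, and adverse event reporting and symptom-oriented examinations continue. These points limit the consequence. They do not supply the missing data or remove temperature from the endpoint.

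**Conclusion.** The gap between endpoint and schedule is real. Followed exactly, the plan gives one of its five named primary safety vital signs no scheduled value after dosing (0 of 7 time points), so the temperature part of the SAP 10.3 change-from-baseline output cannot be filled from scheduled data and no post-dose comparison with placebo is possible.

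This rests on two readings: that Table 6-3 governs the timing of each parameter, as the footnotes direct, and that discretionary readings are not a planned data source. It is an omission between endpoint and schedule, not a contradiction between schedules. The impact is modest, but it should be corrected because values never collected cannot be restored later.

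**What to change.** Reconcile the endpoint lists (Protocol synopsis, Protocol Table 2-1 and SAP Table 2-1), Protocol Table 6-3 and SAP 10.3, in one of two ways:

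- Table 6-3 supplies post-dose temperature at vital-sign contacts that already exist; or
- temperature is removed from the endpoint lists and from the SAP change-from-baseline tables.

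The sponsor decides which. As an optional clarification, split the combined row in Table 6-1 and SAP Appendix A by parameter, so that the marks for temperature and respiratory rate match Table 6-3.

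The cost is text edits to both documents, with the protocol change submitted to the IRB under Protocol 12.2. The first option adds a brief reading at existing contacts and no new visit. The second adds no procedure but leaves a safety endpoint that no longer covers temperature.

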6.1.4.2. Continuous and Spot Oxygen Saturation

Continuous and spot SpO₂ monitoring will be performed as outlined in [Table 6-1](#). Spot SpO₂ will be measured using a portable pulse oximeter placed on the subject's fingertip.

SpO₂ will be monitored for alarms set at <90% continuously up to 1 hour prior to study drug administration and will continue for up to 6 hours following study drug administration, or longer if deemed medically necessary. In addition, SpO₂ will be recorded at the timepoints scheduled in [Table 6-4](#).

Table 6-4. Spot Oxygen Saturation Schedule

Spot Oxygen Saturation - Scheduled Time Points
Screening
Day 1: predose and approximately 1, 2, 3, 4, 6, 7, 8, 10, and 12 hours postdose

6.1.5. 12-Lead Electrocardiogram

Twelve-lead ECGs will be performed as outlined in [Table 6-1](#). Electrocardiogram measurements are further detailed in [Table 6-5](#). Subjects will be in supine position for at least 3 minutes prior to ECG measurements.

Table 6-5. Electrocardiogram Recording Schedule

Electrocardiogram Recording - Scheduled Time Points
Screening
Day -1
Day 1: 1 and 4 hours postdose
Day 2: 24 hours postdose
Day 3: 48 hours postdose
Follow-up visit/End of Study

Windows for ECG assessments are presented in [Table 6-6](#).

Table 6-6. Acceptable Windows for Electrocardiogram Assessments

Elapsed Time	Acceptable Window
> 0 hour and \leq 24 hours	\pm 30 minutes
> 24 hours and \leq 48 hours	\pm 1 hour

6.1.6. Laboratory Evaluations

Laboratory evaluations will be performed as outlined in [Table 6-1](#).

The laboratory evaluations to be conducted for this study are presented in [APPENDIX 6](#). Additional clinical laboratory tests may be performed by the medical laboratory as part of larger standard test panels (not required for subject safety).

The Investigator or delegate in charge will assess each abnormal value to determine if it is clinically significant. Postdose clinically significant laboratory values will be reported as AEs, if applicable, as judged by the Investigator or delegate in charge.

Only test results required by the protocol and/or abnormal results will be entered in the clinical database and reported in the Clinical Study Report, based on report requirement.

6.1.7. Columbia Suicide Severity Rating Scale (C-SSRS)

The C-SSRS is a questionnaire designed for the assessment of suicidal ideation and behavior in adolescents and adults.

To monitor for a history of or for the emergence of suicidal ideation and behavior, subjects will undergo C-SSRS evaluations at the time points indicated in [Table 6-1](#).

The questionnaire must be administered by an Investigator or other individual that is suitably qualified by education or training. See [APPENDIX 7](#) for a sample C-SSRS – Baseline/Screening version assessment and [APPENDIX 8](#) for a sample post-dose C-SSRS (Since Last Visit Version) assessment.

If there is a positive result for suicidality on the C-SSRS after Screening (defined by a subject answering “yes” to questions 4 or 5 on the suicidal ideation portion of the C-SSRS), the subject will be evaluated by an Investigator or medically qualified Sub-Investigator for continuation in the study.

If a subject becomes suicidal during the study, an Investigator or medically qualified Sub-Investigator should provide the appropriate treatment to the subject.

6.1.8. Rescue Therapy

The clinical study site is equipped with emergency equipment and supplies that correspond with the level of risk associated with this study. In case of a medical emergency or an SAE requiring medical intervention, emergency equipment and supplies will be available and will include, but may not be limited to, stocked crash carts, oxygen source, suction pump, and defibrillator. Emergency medication (e.g., naloxone) or rescue medication required for advanced cardiac life support may be administered if deemed necessary by an Investigator or designee. If required, subjects will be transported to a hospital.

The Principal Investigator or designee will be on-site at the time of study drug administration until at least 4 hours postdose. When not available on-site, the Principal Investigator or designee will be on-call until the end of the study. While confined in the clinical site, subjects will be supervised by staff nurses and/or paramedics. Dedicated nurses and/or paramedics will be available to monitor AEs and perform safety measures. The date and time of rescue medication administration as well as the name and dosage regimen of the rescue medication will be recorded.

6.2. Pharmacokinetic Assessments

A total of 15 blood samples will be collected for PK assessments. The complete blood sampling schedule is presented in [Table 6-7](#).

Table 6-7. Pharmacokinetic Blood Sampling Schedule

Sample No	Nominal Time ^a (hours)
01	0.00
02	0.25
03	0.50
04	1.00
05	1.50
06	2.00
07	2.50
08	3.00
09	4.00
10	6.00
11	8.00
12	10.00
13	12.00
14	24.00
15	48.00

a. Nominal times listed are relative to the time of study treatment administration.

Blood samples will be collected by direct venipuncture into a labeled tube containing the appropriate anticoagulant as specified by the bioanalytical facility. As an option to the subject or if judged necessary by the clinical staff, blood samples may be collected from a catheter, which will be placed in the vein of the subject.

The time of PK blood sample collection will be calculated relative to the time of treatment administration. The actual time of all PK blood draws will be recorded and reported for all subjects.

Windows for timed PK blood sample collections are presented in [Table 6-8](#). PK samples collected outside of the pre-specified windows will be documented as protocol deviations. Since actual times are to be used for the PK analysis, deviations will be reflected in the analysis unless indicated otherwise upon review of the data.

Table 6-8. Acceptable Windows for Timed PK Blood Specimen Collection Procedures

Elapsed Time	Accepted Window
Predose	Within 60 minutes prior to study drug administration
> 0 hour to ≤ 30 minutes	± 1 minute
> 30 minutes to ≤ 4 hours	± 2 minutes
> 4 hours to ≤ 12 hours	± 5 minutes
> 12 hours to ≤ 24 hours	± 10 minutes
> 24 hours to ≤ 48 hours	± 2 hours

Mitragynine, 7-hydroxy-mitragynine, paynantheine, speciogynine, and peciociliatine concentrations for PK assessments will be obtained through bioanalysis of the plasma derived from the blood samples drawn during this study, using validated bioanalytical methods.

6.2.1. Pharmacokinetic Sample Processing, Storage and Shipping

Blood samples for PK determination will be processed, stored, and shipped according to the sample processing instructions supplied by the bioanalytical facility.

6.3. Pharmacodynamic Assessments

Pharmacodynamic assessments will be performed throughout the study as outlined in [Table 6-1](#).

Prior to completing the computerized PD measures, all subjects will undergo a scripted training and practice regimen. Eligible subjects who appear to have difficulty differentiating between bipolar and unipolar visual analog scales (VAS) (e.g., making errors such as selecting a score of 50 to indicate the absence of a drug-effect on a unipolar scale) or difficulty distinguishing between "at this moment" and "next-day" measures will undergo additional training on the difference between the scale types. Additional training sessions will be documented in source files.

Testing conditions for PD assessments should remain as consistent as possible. Subjects will be monitored carefully to ensure that they are completing the PD assessments appropriately; all reasonable attempts should be made to rouse subjects who fall asleep during testing cycles. If subjects cannot complete the PD assessments in a timely manner prior to the next required procedure or timepoint due to an AE, testing will be aborted.

